6.2 Toxicity Management

The management of specific AEs and laboratory parameters is described in Table 4 and in the Operations Manual.

The toxicity management of the AEs including AESI consists of safety monitoring (review of AEs on an ongoing basis, and periodical/ad hoc review of safety issues by a safety data monitoring committee), interruption of study drug dosing with appropriate clinical management if applicable, and discontinuation of the subjects from study drug. The management of specific AEs and laboratory parameters is described below.

For subjects who discontinue study drug but continue study participation and are on standard of care therapies, these toxicity management requirements do not apply (including alerts from the central lab) and any intolerability to standard of care therapies should be managed by the prescribing physician.

Serious Infections: Subjects should be closely monitored for the development of signs and symptoms of infection during and after treatment with study drug. Study drug should be interrupted if a subject develops a serious infection or an opportunistic infection. A subject who develops a new infection during treatment with study drug should undergo prompt diagnostic testing appropriate for an immunocompromised subject. As appropriate, antimicrobial therapy should be initiated, and the subject should be closely monitored. Study drug may be restarted once the infection has been successfully treated. Subjects who develop active TB or experience hepatitis B reactivation must be discontinued from study drug. To further monitor subjects for serious infections, subjects will complete at-home weekly temperature monitoring. If above 100.5 degrees Fahrenheit (38 degrees Celsius), subject should inform their study doctor to assess the need for further evaluation.

Canada only: Investigators should be advised to follow local public health guidelines in order to prevent subjects enrolled in these trials from acquiring TB.

Serious Gastrointestinal Events: Subjects presenting with the onset of signs or symptoms of a serious gastrointestinal event should be evaluated promptly for early identification of gastrointestinal perforation. If the diagnosis of gastrointestinal perforation is confirmed, the subject must be discontinued from study drug.

Cardiovascular Events (MACE): Subjects presenting with potential cardiovascular events should be carefully monitored. These events will be reviewed and adjudicated by the independent CAC.

Malignancy: Subjects who develop malignancy other than NMSC or carcinoma in situ of the cervix must be discontinued from study drug. Information including histopathological results should be queried for the confirmation of the diagnosis.

ECG Abnormality: Subjects must be discontinued from study drug for an ECG change considered clinically significant and with reasonable possibility of relationship to study drug OR a confirmed absolute QTcF value > 500 msec.

Management of Select Laboratory Abnormalities: For any given laboratory abnormality, the Investigator should assess the subject, apply the standard of care for medical evaluation and treatment following any local guidelines. Specific toxicity management guidelines for abnormal laboratory values

are described in Table 4 and may require an appropriate supplemental eCRF be completed. All abnormal laboratory tests that are considered clinically significant by the Investigator will be followed to a satisfactory resolution. If a repeat test is required per Table 4, the repeat testing must occur as soon as possible.

Table 4.	Specific 1	Foxicity	Management	Guidelines for	Abnormal	Laboratory	Values
	opeenie	· o/licity	in an agement	Garacinico ior	/ 10/10/11/10/1	Laboratory	- and c

Laboratory Parameter	Toxicity Management Guideline
Hemoglobin	• If hemoglobin < 8 g/dL interrupt study drug dosing and confirm by repeat testing with a new sample.
	 If hemoglobin decreases ≥ 3.0 g/dL from baseline without an alternative etiology, interrupt study drug dosing and confirm by repeat testing with new sample.
	• If hemoglobin decreases ≥ 3.0 g/dL from baseline and an alternative etiology is known, the subject may remain on study drug at the investigator's discretion.
	• If confirmed, continue to withhold study drug until hemoglobin value returns to normal reference range or its baseline value.
Absolute neutrophil count (ANC)	 If confirmed < 1000 cells/µL by repeat testing with new sample, interrupt study drug dosing until ANC value returns to normal reference range or its baseline value.
	 Discontinue study drug if confirmed < 500 cells/µL by repeat testing with new sample.
Absolute lymphocyte counts (ALC)	 If confirmed < 500 cells/µL by repeat testing with new sample, interrupt study drug dosing until ALC returns to normal reference range or its baseline value.
Total white blood cell count	 If confirmed < 2,500 cells/µL by repeat testing with new sample, interrupt study drug dosing until white blood cell count returns to normal reference range or its baseline value.
Platelet count	 If confirmed < 50,000 platelets/µL by repeat testing with new sample, interrupt study drug dosing until platelet count returns to normal reference range or its baseline value.

Laboratory Parameter	Toxicity Management Guideline
Aspartate transaminase (AST) or alanine transaminase (ALT)	 Interrupt study drug immediately if confirmed ALT or AST > 3 × upper limit of normal (ULN) by repeat testing with new sample and either a total bilirubin > 2 × ULN or an international normalized ratio (INR) > 1.5.
	 INR will only need to be measured in subjects with ALT or AST > 3 × ULN by the central lab. A repeat test of INR is not needed for determination if above toxicity management criteria are met.
	 Interrupt study drug immediately if confirmed ALT or AST > 3 × ULN by repeat testing with new sample along with appearance of fatigue, nausea, vomiting, right upper quadrant pain or tenderness, fever, rash, and/or eosinophilia (> 5%).
	 Interrupt study drug immediately if confirmed ALT or AST > 5 × ULN by repeat testing with new sample for more than 2 weeks.
	 Interrupt study drug immediately if confirmed ALT or AST > 8 × ULN by repeat testing with new sample.
	Subjects who meet any of the above criteria should be evaluated for an alternative etiology of the ALT or AST elevation and managed as medically appropriate. The investigator should contact the AbbVie TA MD to discuss the management of a subject when an alternative etiology has been determined. The alternative etiology should be documented appropriately in the eCRF; study drug should be discontinued if no alternative etiology can be found.
	For any confirmed ALT or AST elevations > 3 ULN, complete supplemental hepatic eCRF.
	• Subjects with HBc Ab+ (irrespective of HBs Ab status) and negative HBV DNA at screening who develop the following should have HBV DNA by PCR testing performed within one week:
	• ALT > 5 × ULN OR
	• ALT or AST > 3 × ULN and either a total bilirubin > 2 × ULN or INR > 1.5 OR
	 ALT or AST > 3 × ULN along with clinical signs of possible hepatitis
	• A positive result for HBV DNA PCR testing in these subjects will require immediate interruption of study drug and a hepatologist consultation should occur within one week for recommendation regarding subsequent treatment.
Serum Creatinine	 If serum creatinine is > 1.5 × the baseline value and > ULN, repeat the test for serum creatinine (with subject in an euvolemic state) to confirm the results. If the results of the repeat testing still meet this criterion then interrupt study drug and re-start study drug once serum creatinine returns to ≤ 1.5 × baseline value and ≤ ULN.
	• If confirmed serum creatinine ≥ 2 mg/dL interrupt study drug, and re-start study drug once serum creatinine returns to normal reference range or its baseline value.
	For the above serum creatinine elevation scenarios, complete supplemental renal eCRF.

Laboratory Parameter	Toxicity Management Guideline	
Creatine Phosphokinase (CPK)	 If confirmed CPK value ≥ 4 × ULN (if symptomatic or asymptomatic), complete supplemental CPK eCRF. 	
	 If confirmed CPK ≥ 4 × ULN accompanied by symptoms suggestive of myositis or rhabdomyolysis, interrupt study drug, complete supplemental CPK eCRF, and contact AbbVie Therapeutic Area Medical Director. 	

7 STATISTICAL METHODS & DETERMINATION OF SAMPLE SIZE

7.1 Statistical and Analytical Plans

Complete and specific details of the statistical analysis will be described and fully documented in the Statistical Analysis Plan (SAP). The SAP will be finalized prior to the final (Week 12) database lock. The statistical analyses will be performed using SAS (SAS Institute Inc., Cary, North Carolina, USA). The final analysis will be conducted by AbbVie Statistics group at the final database lock, and the unblinded interim safety reviews will be conducted by the DMC at pre-specified time points as described in Section 7.5, Interim Analysis.

7.2 Definition for Analysis Populations

The Full Analysis Set (FAS) includes all randomized subjects who received at least 1 dose of randomized study drug. The FAS will be used for all efficacy and baseline analyses. Subjects will be grouped according to treatment as randomized.

The Safety Set consists of all enrolled subjects who received at least 1 dose of study drug. Safety analyses are based on treatments actually received.

7.3 Statistical Analyses for Efficacy

Primary Endpoint Analysis

The primary endpoint is change from baseline in DAS28-CRP at Week 12.

The first primary analysis is to test the superiority of ABBV-599 compared to placebo at Week 12.

The second primary analysis is to test a pre-specified set of dose-response models (detailed in the SAP) among ABBV-105 dose groups and the placebo group at Week 12 using the Multiple Comparison Procedure – Modeling (MCP-Mod) method.^{9,10}

Hypothesis testing in the primary analyses will be performed in a ranked fashion based on one-sided significance level of α = 0.05. The other analysis for the primary endpoint includes testing the superiority of ABBV-599 compared to each ABBV-105 dose group, as well as to upadacitinib. Additionally, each ABBV-105 group will be compared vs placebo group. All tests will be performed as

pairwise comparison at one-sided statistical significance level α = 0.05. The listing of these analyses is as follows:

- ABBV-599 vs placebo
- ABBV-105 dose response
- ABBV-599 vs each ABBV-105 dose
- Each ABBV-105 dose vs placebo
- ABBV-599 vs upadacitinib

In the analyses, the treatment mean will be estimated using least squares (LS) mean from Mixed-Effect Model Repeated Measurements (MMRM) method. One MMRM model including all treatment groups up to visit Week 12 data modeling will be used. Comparable historical placebo and upadacitinib data will be used to enhance the statistical power in relevant comparison analyses, which are detailed in the SAP.

Secondary Endpoints Analysis

Continuous efficacy variables will be analyzed using an MMRM method. It will be used for primary inference purpose. Categorical efficacy variables will be analyzed using the Cochran-Mantel-Haenszel (CMH) test controlling for stratification variables. Non-responder imputation (NRI) will be used for primary inference purpose and as observed (AO) analyses will be used for sensitivity analysis for selected endpoints.

Missing Data Imputation Definition

Non-Responder Imputation: An NRI approach will categorize any subject who has missing value for categorical variables at a specific visit as non-responder for that visit. In addition, subjects who prematurely discontinue from study drug will be considered as non-responders for all subsequent visits after discontinuation.

As Observed: AO analysis will not impute values for missing evaluations, and thus a subject who does not have an evaluation on a scheduled visit will be excluded from the AO analysis for that visit. Regardless of treatment switching or premature discontinuation of study drug, all observed data will be used in the analysis.

Observed Case (OC): OC analysis will not impute values for missing evaluations and, thus, a subject who does not have an evaluation on a scheduled visit will be excluded from OC analysis for that visit. In addition, the OC analysis will not use values after premature discontinuation of study drug.

Mixed-Effect Model Repeated Measurements (MMRM): MMRM analysis will be conducted using mixed-effect model with OC analysis. The mixed model includes the categorical fixed effects of treatment, visit and treatment-by-visit interaction, main stratification factors, and the continuous fixed covariate of baseline measurement. An unstructured variance covariance matrix will be used. The parameter estimations are based on the assumption of data being missing at random and using the method of restricted maximum likelihood (REML).

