4 INVESTIGATIONAL PLAN

4.1 Overall Study Design and Plan

This is a 12-week, randomized, double-blind, parallel-group, Phase 2, dose exploratory, multicenter study designed to assess the safety and efficacy of ABBV-105 and ABBV-599 in subjects with active RA who have had inadequate response to bDMARD therapy and are on stable background csDMARD treatment. Subjects who meet eligibility criteria will be randomized in a 3:2:2:2:2:1 ratio to 1 of 6 treatment groups:

- Group 1: Upadacitinib 15 mg and ABBV-105 60 mg administered once daily (QD) (n = 60)
- Group 2: ABBV-105 60 mg and upadacitinib placebo QD (n = 40)
- Group 3: ABBV-105 20 mg and upadacitinib placebo QD (n = 40)
- Group 4: ABBV-105 5 mg and upadacitinib placebo QD (n = 40)

- Group 5: Upadacitinib 15 mg and ABBV-105 placebo QD (n = 40)
- Group 6: ABBV-105 placebo and upadacitinib placebo QD (n = 20)

The study duration will include a 35-day maximum screening period and a 12-week randomized, double blind, parallel-group treatment period with 30-day follow-up. Study visits will be conducted at Screening, Baseline, Week 2, Week 4, Week 8, and Week 12. For post-baseline visits, a visit window of \pm 3 days will be allowed.

The schematic of the study is shown in Figure 1.

The study population will consist of adult subjects who are at least 18 years of age with a diagnosis of RA for \geq 3 months and also fulfill the 2010 ACR/EULAR classification criteria for RA. Subjects will have been treated for \geq 3 months with \geq one bDMARD but continue to exhibit active RA or had to discontinue bDMARD(s) due to intolerability or toxicity, irrespective of treatment duration.

Randomization will be stratified by number of prior bDMARDs used (failed 1 or 2 biologics with the same mechanism of action; failed \geq 3 biologics with the same mechanism of action and/or \geq 2 bDMARDs with different mechanisms of action). Once approximately 35% of the total subjects have been randomized to the second stratum, further screening of subjects in that group may be suspended. See Section 5.1 for information regarding eligibility criteria.

This study will be conducted in approximately 240 subjects with-planned interim safety reviews as discussed in Section 7.5.

Figure 1. Study Design

QD = once daily

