#### Mixed-Effect Model Repeated Measure (MMRM)

MMRM analysis will be conducted for repeated continuous measurements. Data collected after a subject discontinues study drug will be considered as missing. The mixed model includes the categorical fixed effects of treatment, visit and treatment-by-visit interaction, main stratification factors, and the continuous fixed covariate of baseline measurement. An unstructured variance covariance matrix will be used. The parameter estimation is based on the assumption of data being missing at random and using the method of restricted maximum likelihood (REML).

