## 8.3.5 Details for Primary Efficacy Analysis

### 8.3.5.1 Mixed-Effect Model Repeated Measure (MMRM) for Pair-Wise Comparison

In the pair-wise comparison analyses without historical data borrowing, the treatment mean will be estimated from MMRM method. One MMRM model including all treatment groups up to visit Week 12 data will be used.

MMRM analysis will be conducted for primary endpoint. Data collected after a subject discontinues study drug will be considered as missing. The mixed model includes the categorical fixed effects of treatment, visit and treatment-by-visit interaction, prior bDMARD use, and baseline DAS28 (CRP) measurement. An unstructured variance covariance matrix will be used. The parameter estimation will be based on the assumption of data being missing at random and using the method of restricted maximum likelihood (REML).

Least-square mean (SE) and 90% confidence interval (CI) at Week 12 for each treatment group will be presented together with between treatment difference of least-square means (SE), 90% CI and p-value from t-test for the difference = 0.

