#### 8.4 Secondary Efficacy Analyses

Continuous efficacy variables will be analyzed using MMRM method. It will be used for primary inference purpose the same way as for primary efficacy endpoint analysis.

Categorical efficacy variables will be analyzed using the CMH test controlling for stratification variables. The risk difference and 90% confidence intervals for the differences in each comparison will be constructed. NRI imputation will be used for missing data imputation. Point estimate of the response rate for each treatment group will also be summarized with a two-sided 90% confidence interval using Wilson's score method.

In addition, as observed (AO) analyses will be used as sensitivity analyses for DAS28 (CRP) and ACR20/50/70 response rates at all visits.

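### The MMRM uses one baseline slope for all four visits, so the Week 12 adjustment can be off if that slope changes over time; a baseline-by-visit term is a cheap efficiency gain

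*Protocol*

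**What the plan says.** Protocol 7.3 lists the fixed effects as "treatment, visit and treatment-by-visit interaction, main stratification factors, and the continuous fixed covariate of baseline measurement". The general model in SAP 8.2 ends its list in the same way: "main stratification factors, and the continuous fixed covariate of baseline measurement". For the primary endpoint, SAP 8.3.5.1 gives "treatment, visit and treatment-by-visit interaction, prior bDMARD use, and baseline DAS28 (CRP) measurement". In all three places the only interaction with visit is treatment-by-visit, and no other section adds one for baseline.

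The rest of the model is flexible. SAP 8.3.5.1 states: "An unstructured variance covariance matrix will be used". It fits all arms and visits jointly: "One MMRM model including all treatment groups up to visit Week 12 data will be used". The visits are set in Protocol 4.1: "Study visits will be conducted at Screening, Baseline, Week 2, Week 4, Week 8, and Week 12", which gives four post-baseline visits. Only the last of these is primary: "The primary endpoint is change from baseline in DAS28-CRP at Week 12" (Protocol 7.3).

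The same specification reaches further. SAP 8.4 says of the MMRM for continuous secondary endpoints: "It will be used for primary inference purpose the same way as for primary efficacy endpoint analysis". The Week 12 LS means and standard errors also feed the historical-borrowing posterior (SAP Appendix D-3) and, through it, the MCP-Mod analysis (SAP 8.3.5.3).

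**The concern.** The model lets treatment effects and the covariance vary freely by visit but holds the regression of change on baseline equal at every visit. Generalised least squares then fixes that slope as a weighted average over visits, and the weight goes mainly to the early visits if these are less variable. The Week 12 adjustment would be borrowed largely from Week 2.

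If the slope changes between Week 2 and Week 12, two things follow. Some of the precision that baseline adjustment should give at Week 12 is lost, and part of any chance baseline difference between arms stays in the Week 12 estimate. The second matters most for contrasts with placebo, which has 20 patients. An imbalance in that arm is shared by all three ABBV-105 versus placebo contrasts, so it does not average out across doses.

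**Working it through.** **The plan's own figures.** A two-group t-test with SD 1.5 and one-sided 0.05 gives:
- 40 vs 20, difference 0.88: 68.2% (stated 68%)
- 40 vs 40, difference 0.88: 83.0% (stated 83%)
- 60 vs 40, difference 1.0: 94.5% (stated 94%)

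All three reproduce. They use the unadjusted SD and take no credit for baseline adjustment.

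**Inputs from the documents.** SD of change at Week 12 is 1.5; arms are 60/40/40/40/40/20; the planned difference is 0.88; there are four post-baseline visits.

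**Assumed inputs (not in the documents).** Baseline SD 0.8, 1.0 or 1.2. SD of change 1.0, 1.2 and 1.4 at Weeks 2, 4 and 8. Residual correlation 0.75 or 0.85 between adjacent visits, decaying as a power of the lag, or exchangeable 0.6. No dropout. Slopes of change on baseline at Weeks 2/4/8/12:
- constant: -0.30 throughout
- mild: -0.15, -0.25, -0.30, -0.35
- moderate: -0.10, -0.20, -0.35, -0.45
- steep: -0.10, -0.25, -0.45, -0.60
- shrinking: -0.45, -0.35, -0.25, -0.15

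**Formulas.** Let S be the residual covariance and b the vector of visit slopes.
- Common slope: b_c = w'b, with w = S⁻¹1 / (1'S⁻¹1)
- Per-subject variance at Week 12 under the common slope: residual variance + (b_12 − b_c)² × Var(baseline)
- Amount retained in the contrast: (b_12 − b_c) × baseline imbalance
- One-SE imbalance at 40:20: baseline SD × √(1/40 + 1/20) = baseline SD × 0.274

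**Worked case: moderate drift, baseline SD 1.0, adjacent correlation 0.75.**
- Weights on the four visits are about 0.77, 0.02, −0.01 and 0.21, so b_c = −0.174 against −0.45 at Week 12, a gap of 0.276.
- Residual SD with visit-specific slopes: √(2.25 − 0.45²) = 1.431.
- With the common slope: √(1.431² + 0.276²) = 1.457, so the standard error is 1.8% larger.
- Power at 40:20 is 70.4% instead of 71.7%.
- A one-SE imbalance leaves 0.276 × 0.274 = 0.076 DAS28 units, or 9% of 0.88.

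**Range over the nine SD and correlation combinations, ABBV-105 vs in-study placebo (40:20):**

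| Slope pattern | Gap at Week 12 | Increase in SE | Power lost (points) | Left by 1-SE imbalance |
|---|---|---|---|---|
| Constant | 0 | 0 | 0 | 0 |
| Mild | 0.16–0.19 | 0.4–1.2% | 0.3–0.9 | 0.04–0.06 |
| Moderate | 0.27–0.33 | 1.2–3.6% | 0.9–2.7 | 0.06–0.10 |
| Steep | 0.37–0.46 | 2.4–7.2% | 1.8–5.1 | 0.09–0.14 |
| Shrinking (over-adjusted) | 0.26–0.32 | 0.9–3.3% | 0.7–2.4 | 0.06–0.11 |

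**With borrowing.** The placebo prior has SE 0.335, equal to 1.5/√20, so the in-study placebo mean gets about half the weight. The imbalance then scales with √(1/40 + 0.25/20) = 0.194 instead of 0.274, about 29% less. The 0.04 to 0.14 range becomes roughly 0.03 to 0.10.

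**Simulation check** (six arms, 240 subjects, 6,000 runs per scenario; constant, mild and steep slopes). Mean bias of the two models agreed within about 0.001. The common-slope standard error matched its empirical value, and one-sided type I error was 0.045 to 0.052. The Week 12 estimate moved with the baseline imbalance by −0.16 per unit (mild) and −0.38 (steep) under the common slope, as the formula predicts, and by about zero with visit-specific slopes.

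**The case against.** The strongest reply is that a common slope is a legitimate pre-specified choice in a randomised trial that already adjusts for baseline, and that the documents contain nothing to show that slopes drift. That stands. A reader might infer from the model that Week 12 is certainly under-adjusted. The documents do not support this: they give no baseline SD, baseline correlation or visit-specific slope. A constant slope costs nothing, and a shrinking slope gives over-adjustment.

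A reader might also infer that the treatment effect is biased. With complete data it is not, on average. What an imbalance leaves behind is a conditional quantity that the reported standard error already covers. Against the planned standard error of 1.5 × 0.274 = 0.41, a retained 0.04 to 0.14 is about 10 to 34% of one standard error.

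The primary tests are well protected. ABBV-599 versus placebo (60:20, difference 1.88) has power above 99.8% with either model. The MCP-Mod analysis uses the borrowed placebo posterior, which dilutes the imbalance.

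The reply does not remove the main point. Drift in either direction costs some precision, and guarding against it costs almost nothing.

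Dropout is a separate limit. The plan states no rate, and post-discontinuation data are set to missing. In one large simulated trial per scenario, with assumed missing-at-random dropout of 17 to 25% on placebo and 6 to 12% on active, the common-slope model gave a treatment effect 0.01 to 0.08 units larger than the visit-specific model when slopes drifted. This is indicative only.

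**Conclusion.** The specification imposes one baseline slope on four visits, and Week 12 can be mis-adjusted if the true slope varies. Under the assumed inputs, the Week 12 standard error is 0.4 to about 4% larger with mild to moderate steepening and up to about 7% larger with steep drift. A one-SE imbalance at 40:20 leaves 0.04 to 0.14 DAS28 units in the unborrowed contrast. All of this rests on assumed baseline SDs, slopes and correlations; with a constant slope there is no loss.

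It is an efficiency refinement. It does not show that the trial is underpowered: with a constant or steepening slope, common-slope power at 40:20 stays at 69% or more against the stated 68%. Only in the shrinking-slope case do the planned figures slip, and by at most about 2 points (66.3 to 67.7% against 68.2%; 81.4 to 82.7% against 83.0%; 93.6 to 94.3% against 94.5%).

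**What to change.** In Protocol 7.3 and SAP 8.2, 8.3.5.1 and 8.4, add a baseline-by-visit interaction to the MMRM fixed effects for the primary endpoint and every continuous secondary endpoint. Keep the other terms, the unstructured covariance and REML as they are.

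The cost is one model term (3 further degrees of freedom with four visits, in about 240 subjects) and one sentence in the SAP, with no new data. If the slope proves constant, almost nothing is lost. The change should be written in before unblinding, because adding the term afterwards would look data-driven.
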